7. STATISTICAL CONSIDERATION

Statistical analyses will be conducted using SPSS VERSION 23. Qualitative data will be presented in form of frequency and percentage and quantitative data will be presented in form of mean \pm S.D. For the comparison of both treatments (randomly allocated to patients) Wilcoxon test will be applied to compare effectiveness of both treatment plans. P-value ≤ 0.05 will be considered as significant, Baseline characteristics of trial participants will be summarised separately for both randomised group. For each group dichotomous and categorical data of participants will be presented as number and percentages.

The primary outcome, effect of allocation on continuous outcomes that will be assessed both at baseline and at the end of study (e.g. Vitamin-D supplementation at 24 weeks) will be assessed using linear regression, adjusting for the baseline values. The effect of allocation of categorical outcomes variables that will be assessed both at baseline and at the end of study (clinical outcome) will be analysed with generalized linear regression with a log link and binomial distribution to yield a risk ratio adjusted for the baseline

values with 95% CI and p value(**cummings**,2009).. Serum concentration of 25{OH} D will be measured at baseline,05 03 months at baseline, Statistical significance will be inferred where $p < 0.05$.

Allocated to patients) Wilcoxon test will be applied to compare effectiveness of both treatment plans. P-value ≤ 0.05 will be considered as significant.

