(All patients which are not taking vitamin-D Supplementation from last 6 months & having deficiency)

10. Exclusion Criteria

1. pregnant women
2. Patients on active TB medicines
3. Patients do not sign consent form freely

Follow up visits:

11. Treatment obtained:	Yes	No
12. Adverse effects of medicine:	Yes	No
13. Compliance of medicine	Yes	No
14. Outcome of achievement::	Yes	No

Investigator signature:

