- 2.** Human immunodeficiency virus (HIV) is a key challenge for global health. Vitamin D deficiency is common in people living with HIV infection. Antiretroviral therapy (ART) may create unique risk factors for vitamin D insufficiency, including alterations of vitamin D metabolism by ART. Vitamin D supplementation in HIV-infected patients have not previously been investigated in Pakistan and it is unknown whether sufficient physiological levels is associated with improved clinical outcome or not. This statistical analysis plan (SAP) will give more detailed descriptions of the endpoints in the study and the corresponding analyses.

- 3. Study design:** We have designed this study with the hypothesis, that the addition of high dose of vitamin D supplementation would be effective in elevating serum 25-hydroxy vitamin D concentration into normal physiological range in patients with HIV infection and this would improve their clinical outcome over the period of 6 months' treatment. The primary outcome of the study will be the sufficient elevating level of serum 25-hydroxyvitamin D at 24weeks. Secondary outcome of the study will be, the increase means CD4 count, decrease in viral load and improvement in liver function test and to reduce the severity of clinical symptoms. This is a double-blind randomized placebo-controlled trial. 114, patients aged (19-50) years with diagnosed HIV disease will be recruited by purposive sampling technique from VCCT treatment centre of Government Said Mitha Teaching Hospital located in the walled city of Lahore, Pakistan. The patients will be divided into two arms. Arm-A patients will receive recommended ARV + Vitamin D supplements and patients in Arm-B will receive recommended ARV and placebo. Participants will be randomly allocated to receive 25 hydroxy vitamin D supplementation (n=) or placebo (n=) with the start of ART

	Screening	Treatments			
	V 1 Screening & Assessment	V 2 Randomization & 1 st Dose	V 3 2 nd dose	V 4 3 rd dose	V 5 Post Assessments
	-7~1	1 Day	5 week	12 week	24 week
ICF	×				
Eligibility Criteria	×	×			
Baseline Questionnaire	×				
Weight	×		×	×	×
Height	×		×	×	×
Vital Signs	×	×	×	×	×
Vit-D	×			×	
CD4 count	×			×	
Viral load	×			×	
PCR	×			×	
CBC	×			×	
Study Medication		×	×	×	
AE Monitoring		×	×	×	×
RDA					×
End of Study					×

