3.1 Sample size calculation

Assuming that 60% of patients in the control arm would attain > 30% of their baseline vitamin-D status at 6 months, we calculated that a total of 94 participants (47 per arm) would need to complete follow-up in order to detect a 25% absolute increase (to 85%) in the proportion of patients attaining > 30% vitamin-D level at 6 months in the intervention arm with 80% power at the 5% significance level. (Lake, Vitamin D in HIV-Infected Patients on HAART, 2014).

This number was inflated to a total of 114 to allow for attrition due to death and loss to follow-up. No interim analysis was performed. (Shriver, 2019)

4. Aims and objectives:

Primary objectives

1. To determine whether proposed oral high dose vitamin D3 is sufficient for achieving the physiological concentration in HIV positive patients on ART. (primary outcome)

Secondary objectives

1. To determine whether this intervention also improves CD4 count, viral load count, liver enzyme in study participants. (Efficacy outcome).
2. To discover whether this interventional regimen is safe and well tolerated by study participants. (Safety outcome).
3. To ascertain socio-demographics factors responsible for decreased level of vitamin D3 in HIV positive patients on ART.

Tertiary objectives:

1. To conclude the effects of total leucocytes count in HIV patients with vitamin D supplementation.
2. To determine the effects of total neutrophil count in HIV patients with vitamin-D supplementation.
3. To determine the effects of total eosinophil count in HIV patients with vitamin-D supplementation.
4. To conclude the effects of total monocyte count in HIV patients with vitamin-D supplementation.
5. To establish the effects of total platelets count in HIV patients with vitamin-D supplementation
6. To find out the effects of total hemoglobin count in HIV patients with vitamin-D supplementation
7. To determine the effects of total lymphocytes count in HIV patients with vitamin-D supplementation
8. To see if the effects of total HCT count in HIV patients with vitamin-D supplementation

5. Outcomes

This section will present the outcomes investigated to answer the study aims and objectives. The analyses are described in section 6 Analyses.

5.1 Primary outcome:

1. To determine whether proposed oral high dose vitamin D3 is sufficient for achieving the physiological concentration in HIV positive patients on ART. (primary outcome)

5.2 Secondary outcomes:

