6.1 Populations

Intention-to-treat (ITT)

All randomised study subjects. This will be seen as the primary population for the analysis.

Per Protocol (PP)

All randomised study subjects completing the whole study period (complete cases). For a specific analysis, study subjects with missing data on any of the variables in the model will be excluded from the analysis. Analyses of this population is seen as a sensitivity analysis to investigate whether conclusions are sensitive to assumptions regarding the pattern of missing data.

6.2 Groups:

Patients with with vitamin-D deficiency are divided into two groups i.e placebo group and vitamin-D group.

Placebo group: out of total 95 participants 47 participants were on placebo arm

Vitamin-D group:

Similar out of total 95 participants 48 participants were on vitamin-D arm

Vitamin-D deficiency:

All randomized study subjects will be divided into two subgroups according to having vitamin-D deficiency at baseline visit.

Division of groups:

All randomised study subjects will be divided into two subgroups according to treatment.

7. Analyses

All outcomes will be presented using descriptive statistics. As the sample size is low so we will check the normality of each variable on screening (Visit 1) and according to the normality check we will determine the mean difference change in Placebo and active treatment arm.

In descriptive analysis we will mention the mean value of each variable with lower and upper bound with 95% confidence interval, 5% trimmed mean, median, Std. Deviation as per the each group ; normally distributed data by the Mean, Variance, Standard deviation (SD), lower and upper values of the variables to see the outliers if any.

In analytical analysis we will apply T-Test for two independent samples to see the difference between two arms. In case any variable doesn't follow the normality assumptions, we will use non-parametric test.

For the safety objective we will use only frequency/number of events to present it.

SPSS 21 will be used for all statistical analysis.

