7.1 Primary outcome

The primary outcome analysis will be performed to check the difference change in Placebo group and Active Treatment group (Vitamin-D Group) through comparing mean difference from Visit 1 to Visit 4. This test will identify the mean increase or decrease in the Vitamin-D levels in the study Participants.

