7.2 Secondary Outcomes

The secondary outcome analysis will be performed to check the difference change in Placebo group and Active Treatment group (Vitamin-D Group) through comparing mean difference from Visit 1 to Visit 4. This test will identify the mean increase or decrease in the respective variables including CD4 count, PCR detection, Viral Load and Liver Enzymes change.

For the safety objective we will use only frequency/number of events to present it.

For the Socio-Demographic factors association or correlation chi square test or bivariate correlation will be checked with one constant variable (Low Vitamin-D Level on Visit 1).

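### The primary objective and the 60% v 85% sizing concern attaining a vitamin D criterion, but SAP 7.1 tests only mean change and the SAP plans no attainment analysis

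*SAP*

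**What the plan says.** **Objective and hypothesis.** The primary objective (SAP 4, repeated as the outcome in SAP 5.1 and in Protocol 2.1) is "To determine whether proposed oral high dose vitamin D3 is sufficient for achieving the physiological concentration in HIV positive patients on ART". The hypothesis in SAP 3 is that supplementation "would be effective in elevating serum 25-hydroxy vitamin D concentration into normal physiological range". Neither document gives the limit of that range in ng/ml as an endpoint.

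**Sizing.** SAP 3.1 assumes 60% in the control arm and looks for a 25-point increase "in the proportion of patients attaining > 30% vitamin-D level at 6 months", with 80% power at the 5% level. This needs 94 completers (47 per arm), inflated to 114. The same paragraph first words the criterion as relative to each patient's own baseline status.

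**Analysis.** SAP 7 gives a two-sample t-test, or a non-parametric test if normality fails. SAP 7.1 applies this to the change from Visit 1 to Visit 4: "This test will identify the mean increase or decrease in the Vitamin-D levels in the study Participants".

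**Vitamin D categories.** The SAP uses these only at baseline. SAP 6.2 says "All randomized study subjects will be divided into two subgroups according to having vitamin-D deficiency at baseline visit", and the chi-square or correlation analysis in SAP 7.2 relates socio-demographic factors to a low level at Visit 1.

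**Protocol.** Section 7 analyses the primary outcome as continuous, by linear regression adjusted for baseline. It gives a log-binomial risk ratio for categorical outcomes, labelled as clinical outcome. Section 4.4 mentions logistic regression for 25-hydroxy levels without a cut-off. The abstract mentions chi-square for qualitative variables. The Research Performa has a Yes/No item, "Outcome of achievement", which is not defined.

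**The concern.** Whether a dose is sufficient is a question about how many patients end up at or above a limit. A difference in mean change answers another question: whether 25(OH)D rose more on vitamin D than on placebo. A high dose could raise the mean clearly while many patients stay below the limit, or it could bring nearly all of them above it. The planned test can be significant in both cases.

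There is also a mismatch of power. The 80% in SAP 3.1 was worked out for two proportions. A reader would take it as the power of the primary analysis, but SAP 7.1 makes no such comparison, and no SD or expected mean rise is given from which the power of the t-test could be worked out.

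**Working it through.** **1. Reproduce the plan's figure.** Inputs from SAP 3.1: 0.60 v 0.85, 80% power, 5% level (two-sided assumed), equal arms. Unpooled two-proportion formula:

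n = (1.960 + 0.842)² × (0.60×0.40 + 0.85×0.15) / 0.25² = 7.849 × 0.3675 / 0.0625 = 46.15, so 47 per arm and 94 in total.

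This matches exactly. The pooled formula gives 49 per arm. The sizing is a comparison of two proportions.

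**2. Power of a proportion comparison at those rates.** With the 47 and 48 participants in SAP 6.2: 78.9% (pooled normal approximation), 79.5% (chi-square, exact enumeration), 77.5% (Fisher). With 57 per arm (all 114): 85.8%, 86.7% and 81.7%.

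**3. Is the mean test underpowered?** Assumptions, none of them from the documents: the criterion is a level, values are normal with equal SD and equal baselines, and the correlation r between baseline and follow-up is 0.5, with a range of 0.2 to 0.8.

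- Shift implied by 60% v 85%: z(0.85) − z(0.60) = 1.036 − 0.253 = 0.783 SD of the follow-up level.
- SD of change = √(2(1−r)) × SD of level, which equals the SD of level at r = 0.5.
- t-test power with 47 v 48: 96.5% at r = 0.5, 84.7% at r = 0.2, above 99.9% at r = 0.8.

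On these assumptions it is not underpowered.

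**4. What does a significant mean difference say about attainment?** The smallest observed difference that reaches p = 0.05 is t(0.975; 93 df) × √(1/47 + 1/48) = 1.986 × 0.2052 = 0.41 SD of change. In SD of the follow-up level this is 0.52, 0.41 and 0.26 for r = 0.2, 0.5 and 0.8. Active-arm attainment = Φ(z(placebo rate) + shift):

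| Placebo attainment | Just significant, r = 0.5 | Range, r = 0.8 to 0.2 | 1 SD shift | 2 SD shift |
|---|---|---|---|---|
| 10% | 19.1% | 15.3 to 22.2% | 38.9% | 76.4% |
| 30% | 45.3% | 39.5 to 49.6% | 68.3% | 93.0% |
| 60% | 74.6% | 69.5 to 77.9% | 89.5% | 98.8% |

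At the SAP's own 60% control rate, significance can come with a gain of 74.6 − 60 = 14.6 points, against the 25 points used for sizing.

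**5. Is attainment analysed elsewhere?**

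- SAP 6.2 and 7.2: baseline categories only.
- SAP 7.3: blood counts only.
- Protocol 7: "For each group dichotomous and categorical data of participants will be presented as number and percentages" follows directly on the baseline summary. The log-binomial model is for clinical outcome, while vitamin D is the named example for linear regression.
- Protocol 4.4 and the abstract: no endpoint or cut-off.
- Performa item: undefined, and not used in the SAP.

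None of these ties post-treatment 25(OH)D to a limit. The SAP carries over neither regression model.

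**The case against.** **The protocol does have binary methods.** It plans a baseline-adjusted risk ratio with a 95% CI for categorical outcomes, and it mentions logistic regression and chi-square. A reader might infer that no binary method exists at all, and that would be wrong. What stands is narrower: none of these methods is given vitamin D attainment as its endpoint, and the SAP leaves both regression models out.

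**The sized criterion is unclear.** It could be a rise relative to baseline or a garbled level such as 30 ng/ml. A reader might infer that an attainment test in ng/ml is the comparison that was sized. The documents do not establish this. If the criterion is a relative rise, the 60% and 85% rates, the roughly 79% power and the 0.78 SD shift do not carry over to a ng/ml limit. Either reading is still a proportion of patients, so the mismatch with SAP 7.1 remains.

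**SAP 7 reports mean, median, trimmed mean, SD and range by group.** Under a normal model these allow a rough estimate of attainment at any limit. That is neither a count nor a comparison, and it still needs a limit that the SAP does not set.

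**Mean change is a legitimate and more powerful primary test.** This is true, and the protocol itself treats the outcome as continuous. It is a reason to keep the test, but not a reason to leave the stated question without any analysis. The just-significant case in the table is a boundary illustration under assumptions and does not forecast the result.

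**Conclusion.** The point holds. The objective and the sizing concern patients attaining a criterion, SAP 7.1 tests mean change only, and the SAP has no attainment endpoint, cut-off or analysis. Followed as written, the plan would show whether 25(OH)D rose more on vitamin D, but not how many participants reached sufficiency. The 80% power describes a comparison that is not planned.

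That much rests on the text and on the exact reproduction of 47 per arm. The size of the ambiguity (19%, 45% or 75% attaining at the edge of significance) depends on normality, equal SD, equal baselines and a correlation of 0.5, and on placebo rates chosen for illustration.

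A reader might also infer that the planned mean test lacks power. The documents do not support that: with no SD or expected rise stated, power cannot be derived from them, and the illustration gives about 97% (85% to over 99% across the correlations tried).

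This should be changed; the planned comparison itself is not invalid.

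**What to change.** - **SAP 5.1:** before outcome data by arm are examined, set the lower limit of the physiological concentration in ng/ml.
- **SAP 7.1:** add, by arm, the number and percentage attaining that limit at the follow-up sample, with a risk difference (or the protocol's log-binomial risk ratio) and a 95% CI. Show participants with no follow-up value separately, since the primary population is all randomised. Keep the mean-change comparison.
- **SAP 3.1:** state whether the 30% criterion is a rise relative to baseline or a level. Only if it is the level chosen in 5.1 do the 60% and 85% rates, and the roughly 79% power with 47 v 48, apply to the attainment comparison. Otherwise say that the stated power describes neither analysis.
- **Primary analysis:** name which of the two carries the 5% level. This is a trade-off for the sponsor. If outcome data by arm have already been seen, keep mean change as the test and label attainment post hoc.

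**Cost:** SAP wording and one more table from values already collected, with no new samples or visits. The attainment comparison is less powerful than the mean and will be imprecise. With 47 v 48 the 95% CI half-width is 1.96 × √(0.24/47 + 0.1275/48) = 17.3 points at 60% v 85%, and 1.96 × √(0.25/47 + 0.25/48) = 20.1 points at 50% v 50%.

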7.2 Secondary Outcomes

The secondary outcome analysis will be performed to check the difference change in Placebo group and Active Treatment group (Vitamin-D Group) through comparing mean difference from Visit 1 to Visit 4. This test will identify the mean increase or decrease in the respective variables including CD4 count, PCR detection, Viral Load and Liver Enzymes change.

For the safety objective we will use only frequency/number of events to present it.

For the Socio-Demographic factors association or correlation chi square test or bivariate correlation will be checked with one constant variable (Low Vitamin-D Level on Visit 1).

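### SAP 7.2 compares viral load as a mean change with no log scale, detection-limit rule or baseline adjustment; if patients start ART at randomisation, this test has almost no power

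*SAP*

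**What the plan says.** SAP 7.2 analyses the secondary efficacy outcomes "through comparing mean difference from Visit 1 to Visit 4", and says the test will identify "the mean increase or decrease in the respective variables including CD4 count, PCR detection, Viral Load and Liver Enzymes change".

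The test is set in SAP 7: "we will apply T-Test for two independent samples to see the difference between two arms". The fallback is "In case any variable doesn't follow the normality assumptions, we will use non-parametric test", and SAP 7.3 names Mann-Whitney U as the rank test for the tertiary outcomes. The choice rests on the entry values: "we will check the normality of each variable on screening (Visit 1". It does not rest on the changes that are tested.

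The SAP states no transformation for viral load, no convention for results below the assay limit, no baseline covariate and no suppression endpoint.

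Protocol 7 differs. Continuous outcomes measured at baseline and end of study get linear regression adjusted for baseline. Categorical ones get "generalized linear regression with a log link and binomial distribution to yield a risk ratio", also baseline-adjusted. It names a Wilcoxon test as well, and it too gives no log scale for viral load.

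The documents describe entry in two ways. SAP 3 and the Protocol abstract randomise patients as ART begins. Protocol 3, and the primary objective in both documents, describe patients who are on ART.

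**The concern.** Viral load spans orders of magnitude and falls steeply once ART works. On the untransformed scale, a patient whose virus is suppressed changes by almost exactly minus the entry value, in either arm. A patient who only partly responds changes by nearly as much. The arm comparison then mostly reflects how entry viral loads happened to be distributed. Ranking the changes does not help, because their order is the order of the entry values.

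Viral load is a named secondary efficacy outcome in both documents. A true effect of vitamin D on it could be present and this test would be unlikely to show it.

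**Working it through.** **The plan's own power figure.** The only one is in SAP 3.1, and it concerns vitamin D status, not virology: 60% vs 85%, 80% power, 5% significance (two-sided assumed). The unpooled formula gives (1.960 + 0.8416)² × (0.60×0.40 + 0.85×0.15) / 0.25² = 7.849 × 0.3675 / 0.0625 = 46.15, so 47 per arm and 94 in total, as stated. Group sizes used below come from there or from SAP 6.2 ("out of total 95 participants 47 participants were on placebo arm"; 48 on vitamin D). Every viral-load input below is an assumption.

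**Arithmetic for one patient.** Assume baseline log10 with mean 4.7 and SD 0.8, and an assay limit of 50.
- Typical baseline: 10^4.7 = 50,119.
- Suppressed to 50: change −50,069.
- Not suppressed, falling 1.5 log10 to 10^3.2 = 1,585: change −48,534.
- Suppressed and unsuppressed patients differ by 1,535. Baselines one SD either side of the mean run from 10^3.9 = 7,943 to 10^5.5 = 316,228.
- On the log10 scale the same two patients change by −3.0 (4.7 − 1.7) and −1.5, a gap of 1.5 against an SD of 0.8.

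In general, a fall of d log10 removes a share 1 − 10^(−d) of the baseline: 0% for d = 0, 68% for 0.5, 90% for 1.0, 97% for 1.5, 99.0% for 2.0 and 99.9% for 3.0. Once the background fall is large, a further 1 log10 hardly moves the raw change.

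**Simulation A: arms differ in suppression.** All patients are detectable at entry, unsuppressed patients fall 1.5 log10, and the limit is 50. There were 47 per arm (4,000 replicates), repeated with 47 vs 48 (2,000 replicates). Power across the two sets:

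| True suppression | t-test, raw change | Mann-Whitney, raw change | Adjusted log10 | Proportion undetectable |
|---|---|---|---|---|
| 70% vs 90% | 3% | 4-5% | 56-60% | 69-70% |
| 60% vs 85% | 2-3% | 5% | 65-69% | 77-80% |
| 80% vs 95% | 3% | 4-6% | 49-52% | 62-65% |

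Raw change correlated with baseline at about −0.996 or closer to −1. With equal suppression (80% vs 80%) every method rejected in about 5% of runs or fewer.

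**Simulation B: vitamin D adds a further fall.** 47 vs 48, 1,000 runs per scenario, ART started at randomisation. Baseline log10 mean 4.5-5.0, SD 0.5-0.8; residual SD 0.7-1.0.
- Placebo fall 2.0-2.5 log10: baseline explains at least 99% of the variance of the raw change (Spearman −0.99 to −1.00). For an extra 0.5 log10, power is 2-5% (t-test), 4-5% (Mann-Whitney) and 48-92% (adjusted log10). For an extra 1.0 log10 it is 2-4%, 4-6% and 95-100%.
- Placebo fall 1.0 log10 (residual SD 0.7): 5-14%, 13-28% and 91-100% for an extra 0.5-1.0 log10.
- Normality of the Visit 1 values was rejected in essentially every run, so the SAP's rule would lead to the rank test.

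**Already on ART.** Power for an extra 0.5-1.0 log10:
- 50-70% suppressed at entry, viraemic placebo patients falling 0-0.5 log10: baseline explains 17-82% of the variance. Mann-Whitney 15-87%, t-test 5-28%, adjusted log10 39-100%.
- The same, but viraemic patients falling 1.5 log10: Mann-Whitney 5%, adjusted log10 26-93%.
- All viraemic, no background fall: Mann-Whitney 74-100%, adjusted log10 92-100%.

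**PCR detection, read as yes/no.** If everyone is detectable at Visit 1, each patient's change is 0 or −1, and its mean differs between arms by exactly the Visit 4 difference in proportions. In the Simulation A set-up, the t-test on this change had 67-69%, 77% and 62% power for the three rows, within about 2 points of a comparison of proportions run on the same data. With 50% suppressed at entry and 60% vs 85%, it had 24% against 44% for proportions at follow-up. In some other mixed-entry runs it did better than proportions, for example 44% against 15%.

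**The case against.** **The scale is not stated.** The SAP never says untransformed values will be used, and neither document gives a unit for viral load. This stands: the raw scale is inferred from silence. An analyst following the text literally would nevertheless take the recorded values, and Visit 4 results below the assay limit have no rule on either scale.

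**The SAP may not displace the protocol.** It presents itself as giving more detail, so Protocol 7's baseline-adjusted regression could be thought still in force. That is possible, but SAP 7 and 7.2 name a different test for these variables and do not mention the regression. The two are unreconciled. Protocol 7 also ties its risk-ratio model to clinical outcomes without naming PCR.

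**The size depends on who is enrolled.** This stands. The near-zero power belongs to a population starting ART with a substantial fall on placebo. Protocol 3 describes patients on ART, and no eligibility criterion in Protocol 3.1 requires viraemia. With little background fall, the rank test keeps moderate to high power.

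**PCR detection is tested separately.** A reader might infer that it fails in the same way, so that a real gain in suppression would almost surely be reported as no difference. The documents do not support that. SAP 7.2 lists PCR detection beside viral load, and a 0/1 change does not carry the size of the entry viral load. With all patients detectable at entry, it finds a suppression difference about as well as a comparison of proportions.

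**Conclusion.** The point holds for viral load, conditionally. With untransformed values, ART started at randomisation and a large fall on placebo (1.5 log10 in unsuppressed patients, or 2.0-2.5 log10 on average), both SAP tests have about 2-6% power. Baseline-adjusted log10 viral load has roughly 50-70% for suppression differences of 15-25 points, and 48-100% for an extra fall of 0.5-1.0 log10. If patients are already on ART, the loss runs from severe to modest: 15-87% for the rank test against 39-100% where viraemic placebo patients fall 0-0.5 log10. All these figures rest on assumed distributions and group sizes of 47 or 48.

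A reader might also infer bias, with any difference found put down to baseline imbalance. That goes too far: randomisation balances baseline on average, and the tests rejected in about 5% of null runs or fewer. The harm is lost power.

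For PCR detection, what remains is a specification fault. A mean of a yes/no result is reported where Protocol 7 provides a risk ratio, and power can drop in some scenarios where many patients enter suppressed.

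**What to change.** In SAP 7.2:
- Analyse viral load as log10, with values below the assay limit set to one prespecified value, by linear regression on arm and baseline log10 viral load. Report the adjusted difference with its 95% confidence interval, and drop the raw mean-change test for this variable.
- Report PCR detection as the proportion undetectable at Visit 4, using the risk-ratio model of Protocol 7. If everyone is detectable at entry, the baseline term drops out.
- Reconcile SAP 3 and the Protocol abstract with Protocol 3 on whether patients start ART at randomisation or are already on it.

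This changes wording only. It needs no new data and returns to models already named in the protocol. The small cost is that the detection-limit convention must be fixed before the data are analysed.

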If a subject arrived at the site for medical treatment on an unscheduled date due to an AE, a change in concomitant drugs, withdrawal status, or measurement data acquired during the research, all relevant facts were documented as thoroughly as possible in the SD. Unplanned visits did not interfere with a planned study schedule. Unscheduled visits may have happened at the subject's solicitation or when the examiner considered it fundamental. There had been no limitations on the tests done during impromptu visits, and the specialist embraced tests that were reasonable and needed for the subject.

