1. To determine whether this intervention also improves CD4 count, viral load count, liver enzyme in study participants. (Efficacy outcome).
2. To discover whether this interventional regimen is safe and well tolerated by study participants. (Safety outcome).
3. To ascertain socio-demographics factors responsible for decreased level of vitamin D3 in HIV positive patients on ART.

5.3 Tertiary outcome:

1. To conclude the effects of total leucocytes count in HIV patients with vitamin D supplementation.
2. To determine the effects of total neutrophil count in HIV patients with vitamin-D supplementation.
3. To determine the effects of total eosinophil count in HIV patients with vitamin-D supplementation.
4. To conclude the effects of total monocyte count in HIV patients with vitamin-D supplementation.
5. To establish the effects of total platelets count in HIV patients with vitamin-D supplementation
6. To find out the effects of total hemoglobin count in HIV patients with vitamin-D supplementation

7. To determine the effects of total lymphocytes count in HIV patients with vitamin-D supplementation
8. To see if the effects of total HCT count in HIV patients with vitamin-D supplementation

Other blood laboratory parameters

Vitamin-D level, CD4 count, viral Load, PCR, CBC

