5.4 Safety outcomes

Adverse events

Adverse events are reported from the visit 1 till Visit 5.

Concomitant medications

Usage of medications during study period will be recorded.

6. Populations and subgroups to be analysed

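### The SAP summarises safety by event counts alone and gives conflicting adverse-event windows, so the planned output cannot answer its safety and tolerability objective

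*SAP*

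**What the plan says.** The objective (SAP sections 4 and 5.2, and protocol section 2.2) is "To discover whether this interventional regimen is safe and well tolerated by study participants". The only analysis rule for it appears in SAP section 7 and is repeated in 7.2: "For the safety objective we will use only frequency/number of events to present it". The SAP defines no safety population, participant-level count, denominator, interval or criterion for safety. The lower-ranked blood counts, by contrast, are given a 95% confidence interval in SAP 7.3.

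The documents describe the window for adverse events in three ways:

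- SAP 5.4: "Adverse events are reported from the visit 1 till Visit 5". Visit 1 is screening.
- The schedule tables in SAP section 3 and protocol section 6: the row "AE Monitoring" is blank at Visit 1 and marked at Visits 2 to 5. Visit 2 is headed "V 2 Randomization & 1 st Dose" and Visit 5 is at week 24.
- The visit list in protocol section 6.1: adverse events are named only at Visit 5 (Day 14) and Visit 6 (Day 28).

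On recording, the Research Performa has one yes/no item under its follow-up visits, "Adverse effects of medicine". For unscheduled visits, including those caused by an adverse event, the protocol says that "all relevant facts were documented as thoroughly as possible in the SD".

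**The concern.** A safety objective asks what share of people were harmed on each arm and how precisely that is known. An event total answers neither question. It mixes the number of people affected with the number of times each was affected, and no uncertainty is attached to it. A low total, or similar totals in the two arms, could then be read as evidence of safety although an appreciable risk remains compatible with the data.

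The window matters because an analyst who follows SAP 5.4 literally would include events that happened before any dose, while one who follows the schedules would not. The two would report different numbers from the same trial. The yes/no item records neither the event nor its date, so by itself it cannot yield an event count or show which events came before the first dose.

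**Working it through.** **The plan's own figures.** The documents give no safety figure. The one design calculation (SAP 3.1) is for efficacy: 60% versus 85%, 80% power, 5% level. It reproduces with two sides and the unpooled formula: (1.960 + 0.842)² × (0.60×0.40 + 0.85×0.15) / 0.25² = 46.15, so 47 per arm and 94 in all. It says nothing about what safety risk the trial can exclude.

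**Inputs.** Arm sizes of 48 (vitamin D) and 47 (placebo) come from SAP 6.2. SAP 3.1 plans 114 and the protocol abstract 104; an equal split (assumed) gives 57 or 52 per arm. The documents give no adverse-event risks, so every risk below is an assumption.

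**1. A count does not fix the risk.** Suppose 10 events on vitamin D (assumed), with exact 95% limits:

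- from 2 people: 2/48 = 4.2% (0.5% to 14.3%)
- from 5 people: 5/48 = 10.4% (3.5% to 22.7%)
- from 10 people: 10/48 = 20.8% (10.5% to 35.0%)

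If the only source were a yes/no answer at the four monitored visits, one person could contribute at most four. Ten positive answers would then need at least 3 people (10/4 = 2.5, rounded up), and the range would be 3/48 = 6.3% to 20.8%. The ambiguity remains.

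**2. Precision left unstated.** With zero affected participants among n, the two-sided exact 95% upper limit is 1 − 0.025^(1/n):

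- n = 48: 7.4% (one-sided 95%, 1 − 0.05^(1/48) = 6.1%)
- n = 52: 6.8%
- n = 57: 6.3%

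For a difference between 48 and 47 participants, the approximate 95% half-width is 1.96 × √[p(1−p)(1/48 + 1/47)]. That is 8.8, 12.1 and 16.1 percentage points at assumed risks of 5%, 10% and 20%.

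**3. Effect of counting from Visit 1.** The schedules put screening up to 7 days before Day 1, and follow-up runs 24 × 7 = 168 days. At a constant event rate (assumed), screening supplies 7/(7 + 168) = 4% of events. If vitamin D truly doubled the post-dose event rate, the ratio of counts would be (2 + 7/168)/(1 + 7/168) = 2.042/1.042 = 1.96 instead of 2.0. The difference in counts would not change.

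Dilution is material only if screening events are common. Take post-dose risks of 10% and 20% and an equal pre-dose risk b. The any-event risks are then 1 − (1−b)(0.90) and 1 − (1−b)(0.80):

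- b = 5%: 14.5% and 24.0%, ratio 1.66
- b = 10%: 19.0% and 28.0%, ratio 1.47
- b = 20%: 28.0% and 36.0%, ratio 1.29

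Nothing in the documents supports screening risks that high.

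**The case against.** Descriptive safety reporting is a reasonable choice in a trial sized for efficacy, and the SAP promises only to present safety, not to test it. Protocol section 7 adds a general rule: "Qualitative data will be presented in form of frequency and percentage". The word frequency in the SAP could be read to include percentages. This has some force: the plan does not forbid a percentage. But the SAP is the safety-specific text and says only, and a percentage of events is not a percentage of participants.

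A reader might infer several stronger things that the documents do not support:

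- That pre-treatment events are definitely counted. Only SAP 5.4 names Visit 1. Both schedules start at the first dose, and the Performa item belongs to follow-up visits. This is a contradiction, not a settled rule. Events before randomisation are also expected to fall equally on both arms.
- That the yes/no item is the only source. No text says so. Event-driven unscheduled visits are documented separately, and the protocol visit list also records symptoms at Visits 1 to 5.
- That a between-arm safety comparison is planned and biased. None is planned; its absence is the gap.
- That missing denominators distort the comparison through unequal arms. With 48 and 47, arm size matters very little (47/48 = 0.98).
- That the 7.4% limit measures an error. It follows from 48 participants and would be the same under any reporting rule. What the plan lacks is any requirement to state it.

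**Conclusion.** The point stands in this form. Reporting event counts alone cannot answer the safety and tolerability objective, because the same count is compatible with very different shares of participants affected (4.2% to 20.8% in the ten-event illustration) and no precision is attached. With 0 of 48 affected, a risk of up to 7.4% would remain compatible with the data, or 6.3% to 6.8% if the larger planned totals applied. These limits take the SAP's arm sizes as the denominator, which the SAP does not itself specify for safety.

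The adverse-event window has three incompatible descriptions that must be reconciled. The numerical effect of the Visit 1 start is probably small: about 4% of events at a constant rate, balanced between arms, with a slight pull of any ratio towards 1. The larger dilution figures rest on assumed screening risks.

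**What to change.** - **Window.** Reconcile SAP 5.4, both schedule tables and the visit list in protocol section 6.1, so that the safety summary counts events from the first dose (Visit 2) to Visit 5 (week 24). List Visit 1 events separately as baseline.
- **Analysis.** In SAP 7 and 7.2, replace the count-only rule with the number and percentage of participants with at least one event, by arm and treatment received, alongside the event count. Give the risk difference with its 95% CI, and state the denominator used.
- **Recording.** Make sure the adverse-event record at scheduled visits holds at least the event and its onset date, since the yes/no item alone cannot support either the count or the window.

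The cost is one extra table, revised SAP wording, slightly more recording at each visit and a more cautious safety statement. A longer event log, or an upper limit printed beside every mention of safety, is not needed to cure the problem.
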